## 16.2 Regulatory Ethics Compliance

### 16.2.1 Investigator Responsibilities

The Investigator is responsible for ensuring that the study is performed in accordance with the protocol, current International Conference on Harmonisation (ICH) guidelines on good clinical practice (GCP), and applicable regulatory and country-specific requirements.

GCP is an international ethical and scientific quality standard for designing, conducting, recording, and reporting studies that involve the participation of human subjects. Compliance with this standard provides public assurance that the rights, safety, and well-being of study subjects are protected, consistent with the principles that originated in the Declaration of Helsinki, and that the study data are reliable.

### 16.2.2 Independent Ethics Committee or Institutional Review Board

Before the start of the study, the Investigator (or Medicago, where required) will provide the Independent Ethics Committee (IEC)/IRB with current and complete copies of the following documents (as required by local regulations):

- Final protocol and, if applicable, amendments to the protocol;
- Sponsor-approved ICF (and any other written materials to be provided to the subjects);

- IB (or equivalent information) and amendments/addenda;
- Sponsor-approved subject recruiting materials;
- Information on compensation for study-related injuries or payments to subjects for participation in the study, if applicable;
- Investigator's *curriculum vitae* or equivalent information (unless not required, as documented by the IEC/IRB);
- Information regarding funding, name of the sponsor, institutional affiliations, other potential conflicts of interest, and incentives for subjects;
- Any other documents that the IEC/IRB requests to fulfill its obligation.

This study will be undertaken only after the IEC/IRB has given full approval of the final protocol, amendments (if any, excluding the ones that are purely administrative in nature, with no consequences for subjects, data, or study conduct), the ICF, applicable recruiting materials, and subject compensation programs, and Medicago (or its designee) has received a copy of this approval. This approval letter must be dated and must clearly identify the IEC/IRB and the documents being approved. In addition, the Investigator must wait for written confirmation from Medicago (or its designee) that the study can be started.

During the study, the Investigator (or Medicago [or its designee], where required) will send the following documents and updates to the IEC/IRB for their review and approval, where appropriate:

- Protocol amendments;
- Revision(s) to ICF and any other written materials to be provided to subjects;
- If applicable, new or revised subject recruiting materials approved by Medicago;
- Revisions to compensation for study-related injuries or payment to subjects for participation in the study, if applicable;
- New edition(s) of the IB and amendments/addenda;
- Summaries of the study at intervals stipulated in guidelines of the IEC/IRB (at a minimum, annually);
- Reports of AEs that are serious, unlisted/unexpected, and associated with the study drug (when applicable);
- New information that may adversely affect the safety of the subjects or the conduct of the study;
- Deviations from or changes to the protocol to eliminate immediate hazards to subjects;
- Reports of deaths of subjects under the Investigator's care;
- Notification if a new Investigator is responsible for the study at any of the sites;
- Development Safety Update Report and Line Listings, where applicable;
- Any other requirements of the IEC/IRB.

---

At least once a year, the IEC/IRB will be asked to review and reapprove this study. The reapproval should be documented in writing. At the end of the study, the Investigator (or Medicago [or its designee], where required) will notify the IEC/IRB of study completion.

### **16.2.3 Informed Consent**

Each subject who participates in the study must first give written consent according to local requirements after the nature of the study has been fully explained, including the risks and requirements of the study. The consent form must be signed before performing any study-related activity. The consent form that is used must have been approved by regulatory authorities, Medicago, and the reviewing IEC/IRB. The informed consent should be in accordance with principles that originated in the Declaration of Helsinki, current ICH and GCP guidelines, applicable regulatory requirements, and Medicago policy. During the study, subjects will be given any new information that may affect their decision to continue their participation in the study. They will be told that their consent to participate is voluntary and that it may be withdrawn at any time, with no reason given, and without penalty or loss of benefits to which they would otherwise be entitled. Only subjects who are fully able to understand the risks, benefits, and potential AEs of the study and who provide their consent voluntarily will be enrolled.

### **16.2.4 Privacy of Personal Data**

The collection and processing of personal data from subjects enrolled in this study will be limited to those data that are necessary to support the development, registration, and future marketing of the investigational product. The data must be collected and processed with adequate precautions to ensure confidentiality and compliance with applicable data privacy protection laws and regulations. Appropriate technical and organizational measures to protect the personal data against unauthorized disclosures or access, accidental or unlawful destruction, or accidental loss or alteration must be in place. Medicago (or its designee) personnel whose responsibilities require access to personal data agree to keep the identity of study subjects confidential.

## **17 ADMINISTRATIVE REQUIREMENTS**

### **17.1 Protocol Amendments**

Neither the Investigator nor Medicago will modify this protocol without a formal amendment. All protocol amendments must be issued and approved by Medicago, and signed and dated by the Investigator. Protocol amendments must not be implemented without prior IEC/IRB approval or when the relevant competent authority has raised any grounds for non-acceptance, except when necessary in order to eliminate an immediate hazard to the subjects, in which case the amendment must be promptly submitted to the IEC/IRB and relevant competent authority. Documentation of amendment approval by the Investigator and IEC/IRB must be provided to Medicago or its designee.

---

Note that administrative changes may be implemented without prior IRB approval; however, the Investigator or Medicago, as applicable, must notify the IRB of any administrative change and ensure that IRB acknowledges receipt of the administrative changes.

The Investigator is responsible for notifying the IRB of all protocol amendments and ensuring that the IRB has approved any amendments when local IRBs are used. When a central IRB is used, Medicago or its designee will inform the IRB on behalf of the sites.

During the course of the study, in situations where a departure from the protocol is unavoidable, the Investigator or other physician in attendance will contact the appropriate Medicago representative or its designee (see Contact Information pages provided separately). Except in emergency situations, this contact should be made before implementing any departure from the protocol. In all cases, contact with Medicago or its designee must be made as soon as possible to discuss the situation and to agree on an appropriate course of action. The data recorded in the eCRF and source documents will reflect any departure from the protocol, and the source documents will describe this departure and the circumstances that made a deviation necessary.

## **17.2 Regulatory Documentation**

### **17.2.1 Regulatory Approval/Notification**

This protocol and any amendment(s) must be submitted to the appropriate regulatory authorities in each respective country, as applicable. A study may not be initiated until all local regulatory requirements are met.

## **17.3 Source Documentation**

At a minimum, source documentation must be available for the following information:

- Subject identification, eligibility, and study identification;
- ICF discussion and date of informed consent;
- Dates of visits;
- Results of safety and study procedures as required by the protocol;
- Record of all reactions, AEs, respiratory illnesses, ILIs, and associated follow ups;
- Concomitant medication;
- Drug receipt, dispensing, and return records;
- Study drug administration information;
- Date of study completion and reason for early discontinuation of study drug or withdrawal from the study, if applicable.

It is recommended that the author of an entry in the source documents be identifiable.

At a minimum, the type and level of detail of source data available for a study subject should be consistent with that commonly recorded at the site as a basis for standard medical care. Specific

---

details required as source data for the study will be reviewed with the Investigator before the study and will be described in the monitoring guidelines (or other equivalent document).

#### **17.4 Case Report Form Completion**

Electronic case report forms (eCRFs) will be provided for each subject who is randomized and receives a dose of study drug. Screening failures will also be entered in an electronic case report form; data entered should include date of birth and reason for screening failure.

Data must be entered into the eCRFs in English. The Investigator must verify that all data entries in the eCRFs are accurate and correct. All eCRF entries, corrections, and alterations must be made by the Investigator or other authorized study-site personnel.

#### **17.5 Quality Control (Study Monitoring)**

In accordance with applicable regulations, GCP, and Medicago (or its designee) procedures, the site will be contacted prior to the study start to review the protocol and study requirements with the clinical study staff. Medicago (or its designee) will review their responsibilities to satisfy regulatory, ethical, and company (Medicago) requirements.

The Investigator or institution, if applicable, will authorize and provide direct access to all relevant documents to allow review of the appropriate conduct of the study by Medicago's (or its designee's) monitor. The Investigator(s) must allocate their time and the time of their staff to the monitors, discuss any findings or issues, and take appropriate actions to maintain the quality and integrity of the study data and conduct.

Protocol deviations will be reviewed by Medicago (or its designee) to identify any non-compliances likely to have a significant effect on the safety and rights of a subject or the reliability and robustness of the data generated. These deviations will be included in the clinical study report.

#### **17.6 Quality Assurance**

To ensure compliance with GCP and all other applicable regulatory requirements, Medicago (or its designee) may conduct quality assurance assessments and/or an audit of the site. Regulatory agencies may conduct regulatory inspections at any time during or after completion of the study. If an audit or an inspection is conducted, the Investigator and/or institution (if applicable) must agree to grant auditors or inspectors direct access to all relevant documents and to allocate their time and the time of their staff to discuss the conduct of the study and any findings or issues, and to implement corrective and/or preventative actions to address any findings or issues identified.

#### **17.7 Record Retention**

Following closure of the study, the Investigator must maintain all site study records in a safe and secure location. The records must be easily accessible when needed (e.g. for a Medicago [or its designee] audit or regulatory inspection) and must be available for review in conjunction with assessment of the facility, supporting systems, and relevant site staff.

---

When permitted by local laws and regulations or institutional policy, some or all of the records may be maintained in a format other than a hard copy (e.g. scanned electronic). The Investigator must ensure that all reproductions are legible and are a true and accurate copy of the original.

The Investigator must follow the time period for retaining the site records in order to comply with all applicable regulatory requirements. The minimum retention time will meet the strictest standard applicable to a particular site, as dictated by local laws and regulations, Medicago (or its designee) standard operating procedures (SOPs), and/or institutional requirements. The Investigator must contact Medicago (or its designee) prior to the disposal of any study documents at the end of the retention period.

If the responsible Investigator retires, relocates, or, for any other reason, withdraws from the responsibility of keeping the study records, custody must be transferred to another person who will accept the responsibility. Medicago (or its designee) must be notified in writing of the name and address of the new custodian. Under no circumstance shall the Investigator relocate or dispose of any study documents without having obtained prior written approval from Medicago (or its designee).

If it becomes necessary for Medicago or the appropriate regulatory authority to review any documentation relating to this study, the Investigator must permit access to such reports.

## **17.8 Study Completion/Termination**

### **17.8.1 Study Completion**

The study will be considered to be completed with the last contact with the last subject participating in the study. The final data from the investigational site will be sent to Medicago (or designee) after completion of the final subject visit at that site. Investigational sites will be closed after study completion. An investigational site is considered closed when all required documents and study supplies have been collected, all data have been entered, monitored, locked, and signed and a site closure visit has been performed.

### **17.8.2 Study Termination**

Medicago (or its designee) reserves the right to close the investigational site or terminate the study at any time for any reason at the sole discretion of Medicago. Investigational sites will be closed after study termination once Medicago (or its designee) has completed all study related tasks. Reasons for the early closure of an investigational site by Medicago (or its designee) or the Investigator may include, but are not limited to:

- Failure of the Investigator to comply with the protocol, Medicago's (or its designee's) procedures, or GCP guidelines;
- Inadequate recruitment of subjects by the Investigator;
- Discontinuation of further drug development.

The Investigator may initiate site closure at any time, provided there is reasonable cause and

---

sufficient notice is given in advance of the intended closure.

Site closure following an Investigator request can only be performed when all active study subjects have completed the study period, Medicago (or its designee) has collected all required documents and study supplies, and all data have been entered, monitored and locked.

### **17.9 Registration of Clinical Studies and Disclosure of Results**

Study information from this study will be posted on publicly available clinical trial registries in countries where applicable and will include information required by law. In addition, the results summary will be posted to the same clinical trial registries, to the extent specified by law, and will include information required by regulatory authorities.

## 19 APPENDICES

### 19.1 Appendix 1 – Sample Ruler to Measure Local Reactions

Site Reaction Measuring Ruler

Grading for erythema and swelling where the vaccine was given	
Grade 0	None or less than 25 mm
Grade 1	Between 25 mm and 50 mm
Grade 2	Between 51 and 100 mm
Grade 3	More than 100 mm
Grade 4	Skin/tissue loss at the injection site (blister or ulcer formation) of any size

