#### 10.3.1.1 Solicited Local and Systemic Reactions

Subjects will be monitored for both solicited local reactions (erythema, swelling, and pain at the injection site) and solicited systemic reactions (fever, headache, fatigue, muscle aches, joint aches, chills, a feeling of general discomfort, swelling in the axilla, and swelling in the neck) from the time of vaccination through Day 7. While the subjects remain in the clinic following vaccine administration, staff will monitor them for local and systemic reactions; after release from the clinic facility, from the evening of Day 0 to the evening of Day 7, subjects will measure and record their local and systemic reactions in their eDiary.

The intensity of the solicited local and systemic reactions will be graded as: mild (1), moderate (2), severe (3) or potentially life threatening (4) (please refer to [Table 6](#)). Their causal relationship with the study vaccine will be assessed by the Investigator (definitely not related, probably not related, possibly related, probably related or definitely related); see Section [13.1.9](#) for a definition of these causal relationships.

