**Table 6 Severity Grades for Solicited Local and Systemic Reactions**

Symptoms	Severity				
	None	Grade 1 (Mild)	Grade 2 (Moderate)	Grade 3 (Severe)	Grade 4 (Potentially life-threatening)
Injection Site Reactions (Local Reactions)					
Erythema (redness)	< 25 mm	25 - 50 mm	51 - 100 mm	> 100 mm	Necrosis or exfoliative dermatitis
Swelling	< 25 mm	25 - 50 mm and does not interfere with activity	51 - 100 mm or interferes with activity	> 100 mm or prevents daily activity	Necrosis
Pain	None	Does not interfere with activity	Repeated use of non-narcotic pain reliever for more than 24 hours or interferes with activity	Any use of narcotic pain reliever or prevents daily activity	Results in a visit to emergency room (ER) or hospitalization
Solicited Systemic Reactions					
Fever (°C or °F)	< 38.0 °C < 100.4 °F	38.0 - 38.4 °C 100.4 - 101.1 °F	38.5 - 38.9 °C 101.2 - 102.0 °F	39.0 - 40.0 °C 102.1 - 104.0 °F	> 40.0 °C > 104.0 °F

Confidential Information

Symptoms	Severity				
	None	Grade 1 (Mild)	Grade 2 (Moderate)	Grade 3 (Severe)	Grade 4 (Potentially life-threatening)
Headache	None	No interference with activity	Repeated use of non-narcotic pain reliever for more than 24 hours or some interference with activity	Significant; any use of narcotic pain reliever or prevents daily activity	Results in a visit to emergency room (ER) or hospitalization
Fatigue	None	No interference with activity	Some interference with activity	Significant; prevents daily activity	Results in a visit to emergency room (ER) or hospitalization
Muscle aches	None	No interference with activity	Some interference with activity	Significant; prevents daily activity	Results in a visit to emergency room (ER) or hospitalization
Joint aches, chills, feeling of general discomfort or uneasiness (malaise), swelling in the axilla, swelling in the neck	None	No interference with activity	Some interference with activity not requiring medical intervention	Prevents daily activity and requires medical intervention	Results in a visit to emergency room (ER) or hospitalization

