8.8.3 Secondary Endpoints

The secondary endpoints of safety that are mentioned in section 4.2.1 will be analysed as follows:
All safety analyses will be based on the SAS.

Safety and tolerability endpoints (immediate complaints, solicited local and systemic reactions, and TEAEs, deaths, SAEs, AEs leading to subject withdrawal, and NOCDs) will be summarized by treatment group and by age group using descriptive statistics.

The original terms used in the eCRFs by Investigators to identify AEs will be coded using the MedDRA®. All eCRF reported AEs with onset post-vaccination will be included in the safety analyses.

Special attention will be given to those subjects who die, who discontinue from the study due to an AE, who experience an SAE (e.g. summaries, listings, and narrative preparation will be provided, as appropriate), or who experience an allergic or allergic-like reaction (hypersensitivity cases).

Overall summaries of subjects with solicited reactions and Unsolicited Treatment Emergent Adverse Events (TEAE) will be prepared as follows:

- Subjects with any solicited reactions or unsolicited TEAEs
- Any solicited local and systemic reactions occurring 15 minutes after vaccination (immediate complaints)
- Solicited reactions including immediate complaints
- Severe and potentially life-threatening solicited reactions
- Severe and potentially life-threatening related solicited reactions
- Solicited local reactions
- Solicited systemic reactions
- Unsolicited TEAEs (Day 0 to Day 21)
- Related unsolicited TEAEs

- Severe and potentially life-threatening unsolicited TEAEs
- Severe and potentially life-threatening related unsolicited TEAEs
- Serious TEAEs (Day 0 to Day 21)
- Serious TEAEs (Day 0 to End of study)

The percentage of subjects with at least one immediate complaint (local or systemic reactions) and the percent of subjects with at least one immediate complaint of each of the individual local and systemic reactions will be summarized by treatment group and by age group.

In addition, the same summary will be tabulated by maximum severity grading and by causality for each treatment group overall and by age group.

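### The severity grades printed on the subjects' Appendix 1 ruler do not agree with Table 6 / SAP Table 4 for swelling and for Grade 4, and the documents do not reconcile them

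*Protocol*

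**What the plan says.** Protocol Table 6, which SAP Table 4 repeats, grades swelling on two criteria: diameter and effect on activity. Its Grade 1 for swelling is "25 - 50 mm and does not interfere with activity". Grades 2 and 3 can each be reached either by a larger diameter or by a greater effect on activity. Erythema is graded on diameter alone up to Grade 3. Grade 4 is "Necrosis or exfoliative dermatitis" for erythema and necrosis alone for swelling.

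Protocol 10.1.2.3 states that solicited local reactions are graded on the FDA scale as set out in Table 6. It gives each subject a template for measuring redness and swelling in millimetres.

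Appendix 1 (Protocol 19.1) shows that template. It carries a panel titled "Grading for erythema and swelling where the vaccine was given", with one set of grades for both reactions. Grade 1 is "Between 25 mm and 50 mm", Grade 2 is "Between 51 and 100 mm", Grade 3 is anything larger, and Grade 4 is "Skin/tissue loss at the injection site (blister or ulcer formation) of any size". Activity is not mentioned.

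Protocol 10.3.1.1 says that after leaving the clinic "subjects will measure and record their local and systemic reactions in their eDiary". SAP 8.8.3 plans a summary line for "Severe and potentially life-threatening solicited reactions" and tabulations by maximum severity.

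**The concern.** The item that subjects hold while recording their own reactions is headed as a grading scale. For two kinds of reaction it gives a different grade from the scale the protocol names. Nothing in either document says how the two fit together.

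Two uses of the grade are exposed. First, intensity of solicited reactions is a secondary safety endpoint (Protocol 10.3.3.1, SAP 4.2.1), and the scales disagree across the boundary that decides which reactions enter the Grade 3 and 4 summaries. Second, Protocol 10.1.2.3 tells subjects to contact the site for reactions above Grade 2, and Protocol 10.1.3 expects the investigator to be informed of such reactions within 48 hours. The same swelling can lie above that line on one scale and below it on the other.

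**Working it through.** No sample size, power or event count is involved, so the check is a cell-by-cell comparison of Appendix 1 with Protocol Table 6 and SAP Table 4.

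| Reaction | Ruler (Appendix 1) | Table 6 / SAP Table 4 | Agree? |
|---|---|---|---|
| Erythema, Grades 0 to 3 | Below 25, 25–50, 51–100, above 100 mm | Same | Yes |
| Swelling, mm cut-offs for Grades 0 to 3 | Same cut-offs | Same cut-offs | Yes |
| Swelling 25–50 mm, interferes with activity | Grade 1 | Grade 2 | No: ruler one grade lower |
| Swelling 25–50 mm, prevents daily activity | Grade 1 | Grade 3 | No: ruler two grades lower |
| Swelling 51–100 mm, prevents daily activity | Grade 2 | Grade 3 | No: ruler one grade lower |
| Blister or ulcer, no necrosis or exfoliative dermatitis | Grade 4 | None to Grade 3, by size and, for swelling, activity | No: ruler higher |
| Exfoliative dermatitis, no blister or ulcer | Not named | Grade 4 (erythema) | No |

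For swelling Grades 1 to 3 the disagreement is an omission: the ruler leaves out a criterion that is not size. For Grade 4 the definitions themselves differ.

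Example: a 30 mm swelling that prevents daily activity. The ruler places 30 mm in its 25–50 mm band, Grade 1. Table 6 excludes it from Grade 1 because activity is affected, and its activity alternative places it in Grade 3. On the ruler the reaction is outside the Grade 3 and 4 summary and below the contact threshold. In Table 6 it is inside the summary and above the threshold.

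The next question is whether other text settles which grade is analysed:

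- Protocol 10.1.2.3 names Table 6. Its instructions to subjects on local reactions cover the diameter of redness and swelling and an evaluation of pain. They do not mention recording the effect of swelling on activity.
- Protocol 10.3.1.1 gives the causality assessment to the investigator. For intensity it refers to Table 6 but does not say who grades.
- SAP 7.1 derives only demographic and immunogenicity variables. SAP 8.8.3 gives no rule for turning eDiary entries into a reaction grade.

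The intended scale can therefore be identified. What is not stated is whether the activity information it needs for swelling is collected, or that the ruler's grades are to be ignored.

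**The case against.** The strongest reply is that the protocol already names one scale. Protocol 10.1.2.3 and 10.3.1.1 both point to Table 6, and SAP Table 4 repeats it. The template is described as a measuring tool. The instructions for local reactions concern measuring, while the separate instruction on grading concerns systemic reactions. Nothing says that the ruler's grade is entered in the eDiary or analysed, and the appendix is titled a sample.

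Most of this stands. A reader might infer from the mismatch that reactions will be misgraded in the analysis. The documents do not support that, because the eDiary screens are not among them and may already capture activity or compute the grade from Table 6. A reader might also infer a bias between arms. That is not supported either, because all subjects receive the same ruler.

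Two further points limit the consequences. A blister read as Grade 4 from the ruler would prompt contact with the site, so a clinician could review it, although this does not help swelling that is graded too low. And if the limitation of activity comes with pain, pain that prevents daily activity is itself Grade 3 in Table 6, so a subject-level count of severe reactions could be unchanged.

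Naming Table 6 does not remove the problem. Subjects make the record themselves, the item in their hands prints grades that differ from Table 6, and they are told to act on a grade.

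**Conclusion.** The disagreement is in the text and is confined to two places: the missing activity criterion for swelling, and the definition of Grade 4. The effect on recorded grades is conditional on subjects or sites taking the grade from the ruler. In that case, swelling that limits activity is graded one or two grades lower than in Table 6, and a blister or ulcer without necrosis or exfoliative dermatitis is graded higher. The outputs at risk are the severity summaries of solicited local reactions and the contact instruction above Grade 2.

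The number of subjects affected cannot be derived from the documents. Efficacy and sample size are not touched. This is a minor documentation point, worth correcting because the correction is nearly free. Which severity definition is clinically right is not judged here; the passages must be reconciled.

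**What to change.** Either reconcile the Appendix 1 grading panel with Table 6 / SAP Table 4, for both the activity criterion and Grade 4, or remove the grades so that the ruler only measures millimetres. Add one sentence to SAP 8.8.3 stating that the analysed grade of solicited local reactions follows the reconciled Table 6 / SAP Table 4 scale. Protocol Section 12 has the SAP finalised before database lock, which leaves a point at which to do this.

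Check whether the eDiary captured the effect of swelling on activity. If it did not, report that as a limitation in the clinical study report. No redesign of the eDiary is asked for. The cost is a reprint of the ruler text and one SAP sentence.
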